1.0 OBJECTIVES

1.1 Primary Objective

- a. To compare progression-free survival between patients randomized to afatinib in combination with cetuximab versus afatinib alone as first-line treatment for EGFR-mutant NSCLC.

1.2 Secondary Objectives

- a. To evaluate the overall response rate (confirmed and unconfirmed, complete and partial responses) in the subset of patients with measurable disease treated with afatinib plus cetuximab compared to afatinib alone.
- b. To assess the safety of each treatment arm when used in the first-line setting.
- c. To compare time to treatment failure and time to treatment discontinuation (as defined in [Sections 10.5](#) and [10.6](#)) between randomized to afatinib in combination with cetuximab versus afatinib alone.
- d. To compare overall survival (OS) between the arms.

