Preclinical work in mouse models of *EGFR* mutant lung cancer harboring the *EGFR* T790M mutation has shown that the combination of afatinib and cetuximab results in tumor regression, while neither drug alone was effective. (17) These observations led to a Phase Ib/II clinical trial of this drug combination in which patients with *EGFR* mutant lung cancer that was resistant to erlotinib or gefitinib received afatinib 40 mg po daily along with cetuximab at escalating doses starting at 250 mg/m² and increasing up to a predefined maximum dose of 500 mg/m². (18) The dose escalation portion of this trial demonstrated no dose limiting toxicities; therefore the recommended Phase II dose of cetuximab was 500 mg/m² IV q 2 weeks when given in combination with afatinib 40 mg po daily. Results of the first 96 evaluable patients treated in the expansion cohort showed an objective response rate of 30%, with 75% of patients showing partial response or stable disease (Figure 2). (19) The median PFS was 4.7 months. Importantly,

responses occurred in patients with confirmed T790M mutation in their cancers as well as in those that did not have a T790M mutation, which was an unexpected finding given the results of the preclinical studies. Although several other treatment strategies have been pursued in this patient population including erlotinib plus cetuximab and afatinib alone, none have shown the benefit that was seen with the combination of afatinib plus cetuximab. (20,21,22,23) Given the promising results in the resistant setting, we hypothesize that patients may derive an even greater benefit if the combination is used in the upfront, treatment-naïve setting with the goal of delaying the development of resistance.

In the Phase Ib/II trial of afatinib and cetuximab, adverse events resulted in trial discontinuation in 19% of patients (Table 1). It is unknown whether the toxicity will be similar when this treatment is used in the first-line setting.

Table 1. Toxicity in the Phase Ib/II Trial of Afatinib/Cetuximab

Patients with adverse event (n=100)	Grade 1-2	Grade ≥ 3	All grades
Rash/acne, n	79	18	97
Diarrhea, n	64	7	71
Fatigue, n	52	9	61
Nausea, n	50	3	53
Xerosis, n	49	3	52
Stomatitis, n	50	1	51
Nail effect, n	48	0	48

Inclusion of Women and Minorities

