The primary objective for the new design is to compare PFS between the arms at the 1-sided 0.025 level. This analysis would take place when 134 PFS events or 70% of the events among eligible patients have been observed (whichever comes first and will depend on sample size attained). With 134 PFS events, this study has 90% power to detect a hazard ratio of 0.57 (75% improvement). The following table describes the analysis as a function of how many patients are accrued by the time of study closure:

Final Sample Size	# events at analysis	HR with 90% power	improvement in PFS
160	112	0.54	85%
180	126	0.56	78%
200	134	0.57	75%
212	134	0.57	75%

An interim analysis will take place when 64 PFS events have been observed. This analysis will be presented to the SWOG Data and Safety Monitoring Committee at the SWOG Group Meeting closest to this number of events. This analysis will evaluate if there is evidence to recommend early stopping of the study for futility by testing the null hypothesis at the 0.5 level, using a stratified log-rank test. If the p-value is 0.5 or greater, than the recommendation will be that there is insufficient evidence to continue accrual to this study.

Secondary Objectives under the revised design are to compare response rates, OS, time to treatment failure (TTF), time to treatment discontinuation (TTD), and toxicity.

Assuming 212 patients enrolled over 36 months with 14 months of additional follow-up, a one-sided log-rank test with an alpha of 0.025 has 90% power to detect an OS hazard ratio of 0.5, corresponding to a 2-fold increase in median OS, under the exponential distribution. Similarly, if it is assumed that the median TTF is 11 months, and the median TTD is also 11 months, there will be 92% power to detect a 70% increase in medians (hazard ratio of 0.59) for each of these endpoints.

Assuming 85% of patients will have measurable disease, 180 patients will be evaluable for the response comparison between arms. Response rates between the arms will be compared using a chi-squared test of independence at the 1-sided 5% level. With 90 patients per arm, this design has 93% power to detect at least a 22% difference in response rates between the arms and within each arm the rates can be estimated to within 10% with 95% confidence.

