Toxicity rates between arms will be assessed using a chi-squared or Fisher's exact test (as appropriate) at the 1-sided 5% level. Assuming all eligible patients are evaluable for toxicities, rates can be estimated to within 10% with 95% confidence and any toxicity with at least 5% prevalence has almost a 100% chance of being observed. With 106 patients per arm, this design has 92% power to detect at least a 20% difference between the arms.

d. Secondary Objectives

Additional analyses will be to compare response rates, OS, time to treatment failure (TTF), time to treatment discontinuation (TTD), and toxicity.

Assuming 212 patients enrolled over 36 months with 14 months of additional follow-up, a one-sided log-rank test with an alpha of 0.025 has 90% power to detect a OS hazard ratio of 0.5, corresponding to a 2-fold increase in median OS, under the exponential distribution. Similarly, if it is assumed that the median TTF is 11 months, and the median TTD is also 11 months, there will be 92% power to detect a 70% increase in medians (hazard ratio of 0.59) for each of these endpoints.

Assuming 85% of patients will have measurable disease, 180 patients will be evaluable for the response comparison between arms. Response rates between the arms will be compared using a chi-squared test of independence at the 1-sided 5% level. With 90 patients per arm, this design has 93% power to detect at least a 22% difference in response rates between the arms and within each arm the rates can be estimated to within 10% with 95% confidence.

Toxicity rates between arms will be assessed using a chi-squared or Fisher's exact test (as appropriate) at the 1-sided 5% level. Assuming all eligible patients are evaluable for toxicities, rates can be estimated to within 10% with 95% confidence and any toxicity with at least 5% prevalence has almost a 100% chance of being observed. With 106 patients per arm, this design has 92% power to detect at least a 20% difference between the arms.

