14.4 Data Submission Overview and Timepoints

a. WITHIN 7 DAYS OF INITIAL REGISTRATION, SUBMIT:

S1403 Onstudy Form

Baseline Tumor Assessment Form (RECIST 1.1)

Smoking Status Assessment Form

Radiology reports from all scans performed to assess disease at baseline

Pathology report from initial diagnosis

Pathology report from a CLIA-certified lab documenting presence of a sensitizing EGFR mutation

S1403 Local Pathology Review Form (see [Section 18.3](#))

NOTE: Upload radiology reports, pathology reports, and the S1403 Local Pathology Review Form via the Source Documentation: Baseline form in RAVE®.

b. SUBMIT:

Specimens as specified in [Section 15.0](#)

c. WITHIN 14 DAYS AFTER EACH CYCLE OF TREATMENT (1 CYCLE = 28 DAYS), SUBMIT:

S1403 Treatment Form

S1403 Adverse Event Form

d. WITHIN 14 DAYS AFTER EACH DISEASE ASSESSMENT (SEE STUDY CALENDAR FOR SCHEDULE) UNTIL PROGRESSION (AS DEFINED IN SECTION 10.2e), SUBMIT:

Follow-Up Tumor Assessment Form (RECIST 1.1)

Radiology reports from all scans performed to assess disease*. Physician must note tumor measurement in patient records.

*NOTE: Upload reports via the Source Documentation: Follow-up form in RAVE®

e. WITHIN 7 DAYS OF DISCONTINUATION OF PROTOCOL TREATMENT, SUBMIT:

Off Treatment Notice

S1403 Treatment Form

S1403 Adverse Event Form

Smoking Status Assessment Form

f. WITHIN 14 DAYS OF PROGRESSION OR RELAPSE, SUBMIT:

NOTE: IF PATIENT REMAINS ON TREATMENT FOLLOWING PROGRESSION (SEE SECTION 7.6a, CONTINUE TO SUBMIT THE S1403 ADVERSE EVENT FORM AND S1403 TREATMENT FORM AFTER EVERY CYCLE OF TREATMENT AS OUTLINED IN SECTION 14.4c).

Follow-Up Tumor Assessment Form (RECIST 1.1)

Site(s) of Progression/Relapse Form

Radiology reports from all scans performed to assess disease. Physician must note tumor measurement in patient records.

NOTE: Upload reports via the Source Documentation: Follow-up form in RAVE®.

g. ONCE OFF ALL PROTOCOL TREATMENT SUBMIT EVERY 6 MONTHS FOR THE FIRST 2 YEARS AND THEN AT THE END OF YEAR 3:

Advanced NSCLC Follow-Up Form

Late Effects Form (if prior to treatment for progression or relapse or a second primary, and prior to non-protocol treatment, the patient experiences any severe [Grade ≥ 3] long term toxicity that has not been previously reported).

h. WITHIN 4 WEEKS OF KNOWLEDGE OF DEATH:

Notice of Death

If patient was still on treatment, submit materials specified in Section 14.4e; otherwise, submit Advanced NSCLC Follow-Up Form.

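### Toxicity is compared between arms only by ever/never proportions, which measure cumulative burden but cannot separate monthly risk from time on treatment

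*Combined protocol and SAP*

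**What the plan says.** Section 1.2b states the aim: "To assess the safety of each treatment arm when used in the first-line setting". It names no time window and no exposure basis.

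The analysis is in Section 11.2c and is repeated in 11.2d: "Toxicity rates between arms will be assessed using a chi-squared or Fisher's exact test (as appropriate) at the 1-sided 5% level". The denominator is all eligible patients, and the precision statement is that of a simple proportion: "Assuming all eligible patients are evaluable for toxicities, rates can be estimated to within 10% with 95% confidence". Power is given as follows: "With 106 patients per arm, this design has 92% power to detect at least a 20% difference between the arms". Neither section describes a fixed window, a time-to-first-event analysis or an exposure-adjusted rate for toxicity.

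The same sections make treatment duration an endpoint. With an assumed median of 11 months for time to treatment failure and for time to treatment discontinuation (TTD), "there will be 92% power to detect a 70% increase in medians (hazard ratio of 0.59) for each of these endpoints". Sections 7.2 and 7.6 let treatment run until progression, toxicity or another removal criterion. Section 2.0 reports that in the earlier combination trial "adverse events resulted in trial discontinuation in 19% of patients". Section 14.4c ties the S1403 Treatment and Adverse Event Forms to the cycle: "WITHIN 14 DAYS AFTER EACH CYCLE OF TREATMENT (1 CYCLE = 28 DAYS), SUBMIT".

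**The concern.** A patient treated for longer has more time in which to record a toxicity. If one arm stays on drug longer, an ever/never comparison mixes two quantities: the risk per month of treatment and the number of months. If Arm 1 is treated longer because it works, it can look more toxic at the same monthly risk. If Arm 1 stops early because it is poorly tolerated, a higher monthly risk can disappear from the comparison.

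The effect depends on when a toxicity starts. Section 3.2 says cetuximab rash generally begins within two weeks, so it should be little affected. It places hypomagnesemia anywhere from days to months after the start, so that kind of event is exposed to the problem. At stake is what the trial can conclude about the safety of adding cetuximab, because no other between-arm toxicity analysis is planned.

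**Working it through.** **Inputs from Sections 11.2c and 11.2d.** 106 patients per arm; 36 months of accrual plus 14 of follow-up; median TTD 11 months, with 11 × 1.7 = 18.7 months as the alternative; 1-sided 5% test.

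**Assumed, because the documents give no figures.** Exponential TTD, the toxicity hazards, and a data cut at month 50.

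**1. The plan's own figures reproduce.**
- Toxicity power, normal approximation with pooled null variance, 25% vs 45%: null SE = √(0.35 × 0.65 × 2/106) = 0.0655; alternative SE = √[(0.1875 + 0.2475)/106] = 0.0641; power = Φ[(0.20 − 1.645 × 0.0655)/0.0641] = 92.5%. The least favourable case, 40% vs 60%, gives 90.2%. The plan states 92%.
- TTD power: let G(λ) = 1 − (e^(−14λ) − e^(−50λ))/(36λ) be the chance that an event with hazard λ is observed. With μ₂ = ln 2/11 = 0.0630 (Arm 2) and μ₁ = ln 2/18.7 = 0.0371 (Arm 1), G = 0.836 and 0.671. Expected events are 106 × (0.836 + 0.671) ≈ 160. Power = Φ(ln 1.7 × √(160/4) − 1.96) = 91.8%. The plan states 92%.

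**2. Exposure under that alternative.** Mean observed time on treatment is G(μ)/μ: 0.836/0.0630 = 13.3 months in Arm 2 and 0.671/0.0371 = 18.1 months in Arm 1.

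**3. Equal, constant monthly risk h in both arms.** P(ever) = h/(h + μ) × G(h + μ). For h = 2% per month:
- Arm 2: 0.241 × 0.901 = 21.7%.
- Arm 1: 0.350 × 0.809 = 28.4%.
- Rejection probability: Φ[(0.0666 − 1.645 × 0.0595)/0.0593] = 30%.

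| Risk per month | Arm 2 ever | Arm 1 ever | Planned test rejects (formula / simulation) |
|---|---|---|---|
| 0.5% | 6% | 8.5% | 15% / 15% |
| 1% | 12% | 16% | 21% / 21% |
| 2% | 22% | 28% | 30% / 28% |
| 4% | 36% | 46% | 41% / 42% |

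In the same simulations a log-rank test on 28-day cycle of first event rejects in about 5%. If median TTD is only 1.3 times longer (14.3 months), the planned test rejects in 11 to 19% for Arm 2 rates of 10 to 40%.

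**4. Risk that decays with time on treatment, h·e^(−t/τ), equal in both arms.** For Arm 2 rates of 10, 20 and 40%, the planned test rejects in 7, 8 and 10% (τ = 3 months) and 9, 11 and 15% (τ = 6 months). Simulation puts the range at about 7 to 16%.

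**5. Risk confined to the first month.** The shift is under half a percentage point and rejection is about 5.5 to 6%.

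**6. The opposite direction (7-month Arm 1 median and risk ratios assumed).** Arm 2 has a median of 11 months and 2% risk per month. With Arm 1 risk 1.5 times higher, P(ever) is about 22% in both arms; the planned test detects the excess in about 6% of trials and log-rank in about 36%. With doubled risk the figures are about 24 to 28% and 76 to 78%.

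**The case against.** A reader might infer that the planned test fails to hold its 5% level. It does not fail. Its null is an equal proportion of patients ever affected, and for that null the level holds. The rejection rates above arise under a different null, equal risk per month. Cumulative burden is a legitimate answer to objective 1.2b, since patients treated for longer do accumulate more toxicity. This stands, and it is why the planned test should stay.

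A reader might also infer that the plan forecasts unequal durations. It does not. The 70% longer median is an alternative used for power. If TTD turns out similar, the two analyses agree.

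The constant-hazard figures are an upper case. Rash and diarrhea of grade 3 or more were the toxicities of specific focus in Section 11.2a, under the original Phase II interim, and rash starts early. Dose reductions are maintained once made (Section 8.3), which plausibly lowers later risk. The masking case rests on chosen inputs. The 19% discontinuation figure comes from TKI-resistant patients, and Section 2.0 says first-line toxicity may differ.

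The added analysis has limits too. Serum magnesium is scheduled in Arm 1 (Section 9.1) but not in Arm 2 (Section 9.2), and no time-to-event method corrects that. Cetuximab can be stopped while afatinib continues (Section 8.3), so months on treatment are not months on cetuximab. No stopping rule or efficacy claim in the revised design depends on the toxicity test.

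These points limit the size of the problem and argue against replacing the test. They do not supply the missing comparison.

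**Conclusion.** The point holds as a gap in the analysis plan. No stated figure is wrong. The only planned between-arm toxicity comparison answers the burden question and leaves open whether a difference reflects risk per month or time on drug.

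Under the plan's TTD alternative and equal monthly risk, the test would flag a difference in about 15 to 42% of trials for constant risk, about 7 to 16% for risk decaying over 3 to 6 months, and near 5% for first-weeks toxicity. If Arm 1 is treated for less time the bias reverses and can mask an excess. The hazards, their shape and the exponential TTD are assumptions. The direction and size in the actual trial depend on the observed TTD difference. The change is worth making because it is cheap and affects what can be concluded about safety.

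**What to change.** In Sections 11.2c and 11.2d, keep the chi-squared or Fisher's exact comparison and label it the analysis of cumulative burden. For each toxicity tested, add a log-rank comparison of cycle to first occurrence (cause-specific hazard), censored at the end of adverse event reporting. Define that end explicitly, because the calendars in Section 9.0 continue toxicity notation in follow-up while Section 14.4g then calls only for a Late Effects Form in limited circumstances. Report total months on treatment per arm and, for Arm 1, months on cetuximab separately.

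The cost is analysis wording. The forms are already due every cycle, though their fields are not shown, so the cycle of onset is inferred from the submission schedule. There are three downsides to state in the plan:
- Onset is known only to the 28-day cycle.
- Censoring at stopping may be informative, because patients stop for progression, death or another toxicity.
- Unequal ascertainment remains, as with serum magnesium, so such toxicities need a caution in either analysis.

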1.3 Translational Objectives

- a. To investigate the molecular mechanisms that confer benefit from afatinib and afatinib plus cetuximab by evaluating whether the presence of *de novo EGFR T790M* mutation or other molecular alterations in the pre-treatment tumor influence the clinical outcomes
- b. To quantitatively assess whether the ratio of sensitizing *EGFR* (*EGFRs*) mutation to *EGFR T790M* influences outcome and is altered during treatment.
- c. To evaluate the frequency of known mechanisms of resistance to EGFR-directed therapies in the context of afatinib plus cetuximab and afatinib alone treatment.
- d. To identify potential novel predictors of benefit to afatinib plus cetuximab.
- e. To identify potential new mechanisms of resistance to EGFR-directed therapies.
- f. To establish patient-derived xenografts (PDXs) from a subset of patients by re-biopsy at the time of progressive disease for drug testing and genomic analysis.
- g. To assess whether circulating tumor markers can be used as indicators of sensitivity and resistance to afatinib plus cetuximab and afatinib alone.
- h. To determine whether the levels of EGFR protein by immunohistochemistry predict for benefit to afatinib plus cetuximab and afatinib alone.

2.0 BACKGROUND

EGFR Mutation Positive NSCLC

NSCLC is the leading cause of cancer-related death worldwide, and results in over 160,000 deaths in the United States per year. In patients with advanced or metastatic disease, platinum-based chemotherapy had been the mainstay of management with a response rate and median overall survival of approximately 30% and 12 months, respectively. Over the past decade,

identification of oncogenic drivers of NSCLC and targeted therapies that inhibit these drivers have revolutionized the way in which lung cancer is treated. Approximately 15% of all patients with NSCLC harbor a mutation in the Epidermal Growth Factor Receptor (EGFR) gene of the tumor. (1,2,3) Most of these mutations affect small regions of the gene within exons 18 to 21 that code for the EGFR tyrosine kinase domain. The most common mutations result in an in-frame deletion in exon 19 and a point mutation resulting in an amino acid substitution at codon 858 (L858R) in exon 21. There are currently two classes of EGFR-targeted agents with distinct mechanisms of action: monoclonal antibodies against the extracellular domain of this receptor (i.e. cetuximab), and small molecule tyrosine kinase inhibitors (TKIs, i.e. erlotinib, gefitinib, and afatinib) which act as ATP analogues and compete for the tyrosine kinase catalytic site thus interfering with inhibition of receptor activation. EGFR TKIs have revolutionized the way in which NSCLC is treated, as they are extremely effective in treating patients with EGFR-mutated cancers, especially compared to chemotherapy.

First-generation EGFR Tyrosine Kinase Inhibitors (TKIs)

Several large, randomized trials have now shown the benefit of treating patients whose tumor harbors an *EGFR* mutation with gefitinib or erlotinib in the first-line setting compared to chemotherapy. (4,5,6,7) Although there is clearly an advantage to the use of EGFR TKIs as upfront treatment of *EGFR*-mutant NSCLC compared to chemotherapy, resistance typically develops after a median of about one year. The most common molecular characteristic found in tumors at the time of resistance to EGFR TKIs, observed in 50-60% of cases, is acquisition of a secondary mutation in *EGFR*, the T790M mutation that increases the affinity of the kinase for ATP and therefore alters the ability of gefitinib or erlotinib to bind in the ATP-binding site of the receptor. (8) While multiple other mechanisms of EGFR TKI resistance have also been described, including *MET* and *HER2* amplification, no therapeutic strategies to overcome resistance have been approved. (9)

Afatinib in EGFR Mutation Positive NSCLC

[figure not shown]

Figure 1. Progression-free survival in LUX-Lung 3.

[figure not shown]
Afatinib is a second generation, irreversible, ErbB family blocker (ErbB1/EGFR, ErbB2/HER2, and ErbB4/HER4). Afatinib 40 mg po daily as a single agent has been studied in several trials of *EGFR* mutant NSCLC, with improved efficacy compared to chemotherapy. (10,11,12) In the LUX-Lung 3 trial, afatinib improved the response rate from 23% to 56% and prolonged PFS from 6.9 to 11.1 months compared to chemotherapy in treatment-naïve patients with *EGFR* mutation positive NSCLC (Figure 1). (13) Afatinib has also been shown to improve quality of life

compared to chemotherapy. (14) When data from LUX-Lung 3 and LUX-Lung 6 are combined, there is an overall survival (OS) benefit seen with afatinib compared to chemotherapy, with median survival of 27.3 months compared to 24.3 months ($p=0.0374$). (15) This difference is particularly impressive in patients with an exon 19 deletion EGFR mutation, in which median OS is 31.7 months with afatinib compared to 20.7 months with chemotherapy ($p=0.0001$). (16) Although no data currently exists directly comparing afatinib to gefitinib or erlotinib, the activity of this 2nd generation EGFR TKI is likely to be equal to or better than either of the 1st generation TKIs in this setting.

Afatinib Plus Cetuximab in the Treatment of EGFR TKI-resistant NSCLC

Preclinical work in mouse models of *EGFR* mutant lung cancer harboring the *EGFR* T790M mutation has shown that the combination of afatinib and cetuximab results in tumor regression, while neither drug alone was effective. (17) These observations led to a Phase Ib/II clinical trial of this drug combination in which patients with *EGFR* mutant lung cancer that was resistant to erlotinib or gefitinib received afatinib 40 mg po daily along with cetuximab at escalating doses starting at 250 mg/m² and increasing up to a predefined maximum dose of 500 mg/m². (18) The dose escalation portion of this trial demonstrated no dose limiting toxicities; therefore the recommended Phase II dose of cetuximab was 500 mg/m² IV q 2 weeks when given in combination with afatinib 40 mg po daily. Results of the first 96 evaluable patients treated in the expansion cohort showed an objective response rate of 30%, with 75% of patients showing partial response or stable disease (Figure 2). (19) The median PFS was 4.7 months. Importantly,

responses occurred in patients with confirmed T790M mutation in their cancers as well as in those that did not have a T790M mutation, which was an unexpected finding given the results of the preclinical studies. Although several other treatment strategies have been pursued in this patient population including erlotinib plus cetuximab and afatinib alone, none have shown the benefit that was seen with the combination of afatinib plus cetuximab. (20,21,22,23) Given the promising results in the resistant setting, we hypothesize that patients may derive an even greater benefit if the combination is used in the upfront, treatment-naïve setting with the goal of delaying the development of resistance.

In the Phase Ib/II trial of afatinib and cetuximab, adverse events resulted in trial discontinuation in 19% of patients (Table 1). It is unknown whether the toxicity will be similar when this treatment is used in the first-line setting.

Table 1. Toxicity in the Phase Ib/II Trial of Afatinib/Cetuximab

Patients with adverse event (n=100)	Grade 1-2	Grade ≥ 3	All grades
Rash/acne, n	79	18	97
Diarrhea, n	64	7	71
Fatigue, n	52	9	61
Nausea, n	50	3	53
Xerosis, n	49	3	52
Stomatitis, n	50	1	51
Nail effect, n	48	0	48

Inclusion of Women and Minorities

This study was designed to include women and minorities, but was not designed to measure differences of intervention effects. The anticipated accrual in the ethnicity/race and sex categories is shown in the table below.

DOMESTIC PLANNED ENROLLMENT REPORT

RACIAL CATEGORY	Ethnic Categories				TOTAL	
	Not Hispanic or Latino		Hispanic or Latino			
	Females	Males	Females	Males		
American Indian or Alaskan Native	0	0	0	0	0	
Asian	2	3	0	0	5	
Black or African American	7	11	0	0	18	
Native Hawaiian or other Pacific Islander	1	1	0	0	2	
White	87	110	0	1	198	
TOTAL	97	125	0	1	223	

INTERNATIONAL PLANNED ENROLLMENT REPORT

RACIAL CATEGORY	Ethnic Categories				TOTAL	
	Not Hispanic or Latino		Hispanic or Latino			
	Females	Males	Females	Males		
American Indian or Alaskan Native	0	0	0	0	0	
Asian	0	0	0	0	0	
Black or African American	0	0	0	0	0	
Native Hawaiian or other Pacific Islander	0	0	0	0	0	
White	0	0	0	0	0	
TOTAL	0	0	0	0	0	

